2. STUDY DESIGN

This is a multi-center, randomized, double-blind, placebo-controlled study to assess the efficacy, safety, and tolerability of two different weekly subcutaneous (SC) doses of RO7239361 in ambulatory boys with Duchenne muscular dystrophy (DMD).

Eligible subjects will be randomized to receive doses of RO7239361 or placebo (1:1:1 across the three treatment arms). The randomization will be stratified by:

- Age (6 through 7 and 8 through 11)
- Corticosteroid (CS) Regimen: daily (prednisone, prednisolone, or deflazacort) vs intermittent (any non-daily dosing of prednisone, prednisolone, or deflazacort).

[figure not shown]
A separate randomization will be conducted for Japan (N=17) with stratification for age only (6 through 7 and 8 through 11), not CS regimen.

RO7239361 or placebo will be administered weekly. The first three doses (Days 1, 8, and 15) of study medication must be administered at the site. Parents/caregivers will be trained to administer SC injections during the first three dose administrations.

Parents/caregivers who are comfortable with SC administration can administer the injection at home starting at Day 22. Parents/caregivers will be dispensed an approximately 6 week supply of drug in pre-filled syringes (RO7239361 or matching placebo) for weekly study drug/placebo administration to the subject.

After completion of this 48-week double-blind phase, subjects may enter the open-label phase in which all subjects will receive active RO7239361 study drug. Subjects originally randomized to active drug will continue to receive the dose to which they were originally

randomized. Subjects originally randomized to placebo will be randomized to the high or low dose of RO7239361 on Day 1 of the open-label phase. Dose assignment in the open-label phase may be modified based upon emerging safety findings. Subjects entering the open-label phase will remain blinded to their original and current dose assignment. Any subject who discontinues the study early or who does not enter the open-label phase will enter the follow up phase of the study. The follow up phase of the study is up to 24 weeks. Subjects will be monitored for safety at three visits in the follow up phase. If RO7239361 anti-drug antibodies (ADAs) are present at the last on-treatment visit, the subject should provide immunogenicity samples at all follow up visits. Subjects who enter the follow up phase will undergo ADA monitoring during the follow up visits, which will occur at regular intervals for 24 weeks. The study design schematic is presented below.

2.1 PROTOCOL SYNOPSIS

The Protocol Synopsis is in Section 1 of the Protocol (see [Appendix 1](#)).

2.2 ENDPOINTS

2.2.1 Primary Efficacy Endpoint

The primary efficacy endpoint of the study is the change from baseline in the North Star Ambulatory Assessment (NSAA) total score at Week 48.

2.2.2 Secondary Efficacy Endpoints

Secondary efficacy endpoints include:

- Change from baseline at Week 48 in:
 - Functional Testing:
 - 4-stair climb velocity (4SCV)
 - 4-stair climb time
 - Stand from supine velocity
 - 10-meter walk/run velocity
 - Proximal lower extremity flexor (knee extension and knee flexion) strength (kg), measured using manual myometry
 - 6 Minute Walk Distance (6MWD)
 - 95th percentile stride velocity recorded with ActiMyo (in a subset of the overall study population)
 - Observer Reported Outcome:
 - Parent-reported Pediatric Outcomes Data Collection Instrument (PODCI) transfers and basic mobility subscale
- No change/improvement in clinical impressions as measured by Clinical Global Impression of Change (CGI-C) at week 48.

2.2.3 Exploratory Efficacy and Pharmacodynamic Endpoints

Exploratory efficacy endpoints include:

- Change from baseline at Week 48 in:
 - Performance of Upper Limb (PUL) total score
 - Pulmonary Function Tests (PFTs), including forced vital capacity (FVC) % predicted, forced vital capacity (FVC), forced expiratory volume in 1 second (FEV1), maximal expiratory pressure (MEP), maximal inspiratory pressure (MIP), cough peak flow (CPF), and peak flow rate (PFR)
 - Parent reported PODCI global score
 - Strength of shoulder abductors, elbow flexors, elbow extensors, hip abductors, grip, and pinch, measured by manual myometry
 - Health Utilities Index III utility score
 - Parent-reported Pediatric Quality of Life Inventory Family Impact Module (PedsQL FIM) total score
 - Parent-reported Pediatric Quality of Life Multidimensional Fatigue Scale (PedsQL MFS) global score, in a subset of subjects
 - Serum concentrations of creatine kinase

- ActiMyo additional measures of activity level (other than 95th percentile of stride velocity) and falls (in the subset of the overall study population using the ActiMyo device)
- Cardiac MRI measures
- Number of falls while on study treatment, as recorded in the subject's diary.
- Proportion of subjects with no change/improvement in Caregiver-reported Global Impression of Change (CaGI-C) on DMD symptoms, physical ability, ability to perform daily activities, social life, emotions and mental well-being and overall health, in a subset of subjects
- SPITFIRE Video Assessments of quality of movement scores
- Distribution of CaGI-C responses at week 48
- Percentage change from baseline at Week 48 in:
 - Serum free myostatin and myostatin-drug complex
 - Dual x-ray absorptiometry (DXA) measures of lean body mass, fat mass, and bone mineral density.

2.2.4 Safety Endpoints

- Incidence of treatment-emergent adverse events (AEs)
- Change from baseline in vital signs, electrocardiogram (ECG), and echocardiogram measures
- Change from baseline in safety laboratory measures
- Incidence of marked laboratory abnormalities, based on Roche Standard Reference and Marked Reference Ranges.

2.3 DETERMINATION OF SAMPLE SIZE

The sample size of 159 subjects (53 subjects per arm) will provide 80% power for testing the null hypothesis of no difference between a dose of RO7239361 and placebo, and 90% power for testing the null hypothesis of no difference between the pooled doses of RO7239361 and placebo, at a 2-sided α -level of 0.05 in the change from baseline in NSAA total score at 48 weeks, under the following assumptions:

- A true treatment difference (RO7239361 minus placebo) of 2.5 points
- A standard deviation of 4.4 points
- A treatment discontinuation rate of 5%.

For this study design and analysis, the minimum detectable difference is approximately 1.53 points for the comparison of the pooled dose groups to placebo, and 1.75 points for the comparison of an individual dose group to placebo.

2.4 ANALYSIS TIMING

The primary analysis of efficacy and safety will be conducted when all subjects have completed the 48-week double-blind treatment period.

A futility analysis will be conducted when at least 30% of the total number of subjects have completed 48 weeks of double-blind, placebo-controlled treatment.

An additional efficacy and safety data analysis will be conducted at Week 96 (at the end of the first 48 weeks of the open-label phase of the study).

A final data analysis will be conducted when the study conduct (double-blind and open-label treatment periods) is complete and the database is locked.

3. STUDY CONDUCT

Significant protocol deviations identified by site monitor or site manager will be provided by the protocol manager who is responsible for study management. The following protocol deviations will be defined as relevant protocol deviations (RPDs) and listed. It should be noted, for the RPDs that occur after treatment initiation (RPDs #5 #6 #7), subjects are still under consideration and included in the per-protocol analysis until the time point that the protocol deviations started.

1. DMD not confirmed by medical history (e.g., onset of clinical signs or symptoms before 5 years of age together with an elevated serum creatine kinase level) and by genotyping;
2. Subject not male or not ≥ 6 to < 12 years of age at randomization;
3. Subject not on CS for ≥ 6 months (182 days) prior to randomization;
4. No established 4 stair climb ≤ 8 seconds prior to randomization;
5. Treatment with prohibited medication (listed in Section 7.7.1 of Protocol) for ≥ 7 days at any time during the study or during the 3-month period prior to initiation of study treatment;
6. Dosing that deviates $\geq 20\%$ of the intended dose for > 2 weeks (> 2 doses). This addresses subjects getting the correct treatment, but not the correct dose
7. Incorrect treatment received for ≥ 2 weeks (> 2 doses). This addresses incorrect allocation of subject to active or control and missed doses.

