#### *Use of Corticosteroids:*

As CS have demonstrated benefit on motor function in boys with DMD, boys included in this study will be required to be on a CS (e.g., prednisone/prednisolone or deflazacort) for at least 6 months prior to the start of study treatment, with no significant change in dosage or dosing regimen for at least 12 weeks prior to the start of study treatment. The goal of this inclusion criterion is to control variability in motor function and strength stemming from CS use.

Both prednisone/prednisolone and deflazacort have been shown to be effective in increasing and preserving muscle strength in DMD supporting this pharmacotherapy as an important standard of care. Following initiation of CS, a period of improvement in muscle strength is often observed. To control this potential source of variance, inclusion in this initial study will be restricted to patients who have been taking CS for at least 6 months, plan to continue CS for the duration of the double-blind phase of the clinical trial, and have not had a significant change in dose in the 12 weeks preceding initiation of study treatment.

*Use of Translarna (Ataluren), Exon-Skipping Therapies, or Investigational Agents:*

Subjects receiving Translarna (ataluren), exon skipping therapies (e.g., Exondys51 [eteplirsen]), or investigational agents will not be eligible for this study. The magnitude and time course of treatment response to these agents in DMD is not well understood. Similarly, limited data are available regarding the safety and tolerability of investigational agents. These information gaps render controlling for potential effects of these drugs challenging and thus could complicate interpretation of the data emerging from this study. To avoid a potentially confounding impact of poorly understood effects of ataluren, patients receiving this treatment currently or within 12 weeks prior to the start of study treatment will be excluded from participation. Patients receiving treatment with any (approved or investigational) exon skipping therapies within 6 months prior to the start of study treatment will also be excluded from participation. *Treatment with deflazacort as part of CS dose-finding trials is allowed, as long as the patient has been on treatment for 6 months without significant dose changes 12 weeks prior to study start.*

*Heart Failure:*

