### 2) Type of Participant and Target Disease Characteristics

- a) Males,  $\geq 6$  to  $< 12$  years of age at time of randomization
- b) Diagnosis of *DMD*, confirmed by medical history (e.g., onset of clinical signs or symptoms before 5 years of age together with an elevated serum creatine kinase level observed before or after initial diagnosis) and by genotyping
- c) Participants  $\geq 15$  kg
- d) Ambulatory without assistance
- e) Participants must be receiving corticosteroids (prednisone, prednisolone, or deflazacort) for at least 6 months prior to the start of study drug, with no significant change in dosage ( $> 0.2$  mg/kg prednisone or  $> 0.24$  mg/kg deflazacort) or dosing regimen for at least 12 weeks prior to the start of study drug, with the expectation that dosage and dosing regimen will not change significantly for the duration of the study.
- f) *NSAA score  $\geq 15$  points at screening*
- g)  $4SC \leq 8$  seconds at screening
- h) Subjects must agree to avoid major changes in their physical or respiratory therapy regimen during the double-blind phase, to the extent possible

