4.7.1.3 Corticosteroid Treatment

Subjects must be receiving CS (prednisone, prednisolone, or deflazacort) for at least 6 months prior to the start of study drug, with no significant change in dosage (> 0.2 mg/kg prednisone or > 0.24 mg/kg deflazacort) or dosing regimen for at least 3 months prior to the start of study drug, with the expectation that dosage and dosing regimen will not change significantly for the duration of the study.

For subjects where the dosing frequency is specified, calculated daily dose of CS at baseline will be summarized. Baseline is defined as the last regimen period before the first dose of study drug. Also, a listing of subjects with absolute change in CS ($[\text{calculated daily dose}]/[\text{body weight}]$) from baseline > 0.2 mg/kg prednisone or > 0.24 mg/kg deflazacort will be provided specifying their date and direction of change (increase or decrease). In case of a post-baseline change in CS drug, the following relationship will be used to calculate change from baseline:

1 mg prednisone = 1 mg prednisolone = 1.2 mg deflazacort

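### The SAP's relevant-deviation list takes up the 6-month corticosteroid rule but not the 12-week stability rule, so boys who breach that eligibility rule stay in the per-protocol analysis

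*SAP*

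**What the plan says.** Protocol 6.1, criterion 2e, has three parts on CS: use for at least 6 months; no significant change in dose (more than 0.2 mg/kg prednisone or 0.24 mg/kg deflazacort) "or dosing regimen for at least 12 weeks prior to the start of study drug"; and an expectation at entry that neither will change significantly on study. Protocol 3.1.2 gives the reason: "The goal of this inclusion criterion is to control variability in motor function and strength stemming from CS use".

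SAP Section 3 defines the RPDs. RPD 3 reads "Subject not on CS for ≥ 6 months (182 days) prior to randomization". No other RPD names CS. SAP 4.1.4 builds the per-protocol population from the RPD list and also removes boys with a baseline NSAA below 15.

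SAP 4.7.1.3 restates the stability rule and its thresholds. For changes on study it plans "a listing of subjects with absolute change in CS" above those thresholds, with date and direction.

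Protocol 10.3.1 says the sensitivity analyses will include a per-protocol MMRM. SAP 4.4.4 says only that such analyses may be done, for selected continuous endpoints.

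**The concern.** CS is the background treatment that the protocol itself describes as benefiting motor function, and the 12-week rule exists to keep CS-driven variation out of the motor outcome. RPDs 1 to 4 are all eligibility failures that remove a boy from the per-protocol set. A breach of the 12-week rule is the same kind of failure, from the same criterion as RPD 3, but it removes nobody. A boy whose CS dose was significantly changed two weeks before Day 1 would count as per-protocol through Week 48.

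On-study changes are a separate matter. CS is not supplied by the sponsor and is obtained by ordinary prescription, so its use could drift differently between arms. The plan would not show this in any table. What is at stake is how far the per-protocol result, and the description of background treatment, can be relied on when reading the primary result.

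**Working it through.** **1. Criterion 2e against the SAP**

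| Part of criterion 2e | RPD in SAP Section 3 | Other SAP handling |
|---|---|---|
| CS for at least 6 months | RPD 3 | none needed |
| Stable dose and regimen, 12 weeks before study drug | none | rule restated in 4.7.1.3; no output on breaches |
| Expectation of stability on study | none | listing in 4.7.1.3 |

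**2. Could another RPD fill the gap?** The RPDs that can arise after treatment starts are identified in "for the RPDs that occur after treatment initiation (RPDs #5 #6 #7), subjects are still under consideration".

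- RPD 5: "Treatment with prohibited medication (listed in Section 7.7.1 of Protocol) for" at least 7 days. Protocol 7.7.1 does not list a change in, or stopping of, background CS. Its catch-all item on other drugs could at most touch a newly added drug.
- RPD 6: "This addresses subjects getting the correct treatment, but not the correct dose". It is counted in weekly doses, so it concerns study drug.
- RPD 7: "This addresses incorrect allocation of subject to active or control and missed doses". This too concerns study drug.

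None reaches a CS dose change, regimen change or stop.

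**3. Could another analysis fill it?** The primary model adjusts for CS stratum (SAP 4.4.1), which is fixed at randomization. Subgroups may use baseline CS regimen (4.4.5). The ANCOVA and multiple-imputation analyses (4.4.4) address missing data. None uses a change in CS.

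**4. What the listing misses.** A boy is listed if the absolute change in daily dose per kg exceeds 0.2 mg/kg prednisone (or 0.24 mg/kg deflazacort; 0.2 x 1.2 = 0.24).

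- Stop from dose d: change = |0 - d| = d. At d = 0.2, the test 0.2 > 0.2 fails, so the stop is not listed.
- Switch from D every day to 2D on alternate days: average = 2D/2 = D, change = 0, not listed. This assumes the calculated daily dose averages over days off; the SAP does not define it. Daily versus intermittent regimen is a randomization stratum.

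**5. Power, as background only.** Inputs from SAP 2.3: difference 2.5, SD 4.4, 53 per arm, 5% discontinuation, two-sided 0.05.

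- Evaluable per arm: 53 x 0.95 = 50.35.
- SE = 4.4 x sqrt(2/50.35) = 0.877.
- Power = Phi(2.5/0.877 - 1.96) = 81.4%, consistent with the stated 80%.

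The point does not depend on this figure. It serves only to price the fix. If the added rules removed 5%, 10% or 20% of boys per arm (assumed; the documents give no rate), 47.8, 45.3 or 40.3 per arm would remain. Per-protocol power for 2.5 points would then be about 79%, 77% or 72%, with the SD held at 4.4.

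**The case against.** Four objections have force.

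- *The RPD list is selective by design.* The protocol leaves the definition of major violations to the SAP. Other eligibility rules, such as those on FVC, fractures, body weight and long-off-period CS regimens, are not RPDs either. That is fair. But the SAP took up half of one criterion, and the half it left out is the part meant to protect the motor outcome.
- *On-study stability is only an expectation at entry.* A reader might infer that any later CS change is a protocol violation that the per-protocol set wrongly keeps. The documents do not support that. CS change is neither a prohibited treatment in Protocol 7.7.1 nor a stated reason for discontinuation in 8.1, and is better described as an intercurrent event. SAP 4.4.4 expects no other frequent intercurrent events that matter and adopts a treatment-policy estimand. Its only example is rescue medication, so how CS changes are classed remains unstated. The objection does not touch the 12-week rule, which is a plain entry requirement.
- *Cutting data at a CS change can mislead.* If CS is changed because a boy is declining, removing his later data depends on outcome, possibly unequally by arm. This stands, and it limits the fix.
- *CS use is not ignored.* SAP 4.7.1 summarizes non-study medications and 4.7.1.3 summarizes baseline CS dose. Neither shows change by arm.

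**Conclusion.** The omission is real but modest. The 12-week stability rule is missing from the RPD list, so a boy who breaches it stays in the per-protocol MMRM. On-study CS change is listed, incompletely, and feeds no analysis. This concerns one sensitivity analysis and a descriptive output; the mITT treatment-policy primary analysis is unaffected.

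No size can be put on it. A reader might infer a masked treatment effect or lost power. Any shift would equal the between-arm difference in the share of boys changing CS times the NSAA effect of that change, and the documents give neither. Assumed imbalances of 5 to 15 percentage points and effects of 1 to 3 points give anything from 0.05 to 0.45 points, which is a range of guesses and not an estimate. Any such loss would also sit in the primary comparison, which the fix rightly leaves alone.

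A reader might also take the per-protocol MMRM to be the plan's test of whether the NSAA result depends on CS. Neither document gives it that role.

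The conclusion on the 12-week rule rests on the text alone. The switch example rests on the averaging assumption stated in the working.

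**What to change.** - **Baseline RPD.** Add to SAP Section 3 a significant CS dose change (the existing thresholds of more than 0.2 mg/kg prednisone or 0.24 mg/kg deflazacort) or a regimen change in the 12 weeks before first dose. SAP 4.7.1.3 restates this window as 3 months; reconcile it with criterion 2e before programming.
- **Listing.** Extend 4.7.1.3 to every CS stop and, where dosing frequency is recorded, every daily/intermittent switch. Define the calculated daily dose for intermittent regimens, say what is done when frequency is missing, and tabulate the listing by arm and direction.
- **On-study changes.** State in the SAP how they are classed. If per-protocol data are cut at the change, as for RPDs 5 to 7, report that as a supplementary analysis resting on a missing-at-random assumption. Also settle whether a post-baseline RPD truncates a boy's data (Section 3) or excludes him (4.1.4, which requires no RPD through Week 48), and correct the reference in 4.1.4 from Section 2.4 to Section 3.
- **Primary analysis.** Leave unchanged.

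The cost is SAP wording and minor programming. CS is reviewed at every double-blind visit and recorded in a caregiver diary. The downsides are a slightly smaller per-protocol set and, if on-study data are cut, possible outcome-dependent censoring.

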RO7239361 also binds to growth and differentiation factor-11 (GDF-11), which has been implicated in heart failure associated with aging in mice. However, this finding is controversial.  Although the mechanism underlying the development of aging-related re-modeling of the heart likely differs from that underlying the development of heart failure in DMD, potential cardiac effects of RO7239361 will be monitored in subjects enrolled in this study using echocardiography. Notably, there have been no cardiac findings in animals that received RO7239361 in completed or ongoing toxicology studies. In order to clearly differentiate any potential effects of RO7239361 on heart function from cardiac manifestations of disease progression, it is prudent to exclude patients with uncontrolled cardiac failure. It is requested that potential participants with ejection fraction <55% at baseline be discussed with the Sponsor's Medical Monitor.

*Use of Growth Hormone or Androgens:*

Growth hormone may exert effects on cardiac morphology and function, while androgens may alter skeletal muscle function in boys with DMD. To avoid potential confounding effects of growth hormone and androgens on the endpoints being measured in this study, patients receiving these treatments currently or within 12 weeks or 5 half-lives (whichever is longer) prior to the start of study treatment will be excluded from participation.

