## **2) Prior/Concomitant Therapy**

- a) Any change (initiation, change in drug class, dose modification unrelated to change in body weight, interruption or re-initiation) in prophylaxis/treatment for CHF within 12 weeks prior to start of study treatment
- b) Any change (initiation, change in drug class, dose modification unrelated to change in body weight, interruption or re-initiation) in prophylaxis/treatment for bone density within 12 weeks prior to start of study treatment
- c) Participants on intermittent CS regimens with off periods of 20 days or longer (e.g., 10 days on, 20 days off)
- d) Treatment with exon skipping therapies within 6 months prior to the start of study drug administration.
- e) Treatment with ataluren *currently or within 12 weeks prior to the start of study drug administration*
- f) *Treatment with any other investigational drug (excluding deflazacort in CS dose-finding trials) currently or within 12 weeks prior to the start of study drug administration*
- g) Current or prior treatment within 12 weeks prior to the start of study drug administration with androgens or human growth hormone.
- h) *Concurrent or previous participation at any time in a gene therapy study*
- i) Prior treatment with RO7239361 or any other anti-myostatin agent

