### **7.7 Concomitant Therapy**

#### **7.7.1 Prohibited and/or Restricted Treatments**

Prohibited and/or restricted medications taken prior to study drug administration in the study are described below. Medications taken within 4 weeks prior to study drug administration must be recorded on the CRF. Prior therapies to treat DMD, including CS, should be reported on the CRF, regardless of when the prior therapy was administered. Routine standard of care immunizations should be maintained throughout the study.

Experimental medications to treat DMD may be permitted during the *OL* phase. This will be dependent upon results from the double-blind phase.

- 1) Prior exposure to RO7239361 or any other anti-myostatin agent.
- 2) Treatment with ataluren *within 12 weeks prior to the start of study drug administration*.
- 3) *Treatment with any other investigational drug (excluding deflazacort in CS dose-finding trials)* currently or within 5 half-lives prior to the start of study drug administration. If the half-life of the prior treatment is unknown, the investigator must consult with the Roche medical monitor to determine the washout duration.
- 4) Treatment with exon skipping therapies within 6 months prior to the start of study drug administration
- 5) Current or prior treatment within 12 weeks of study drug administration with androgens or human growth hormone.
- 6) Concomitant or previous participation at any time in a gene therapy study.
- 7) Use of any other drugs, including over-the-counter medications and herbal preparations, within 1 week prior to start of study drug administration or during study participation except those medications cleared by the Roche medical monitor.

Any concomitant therapies must be recorded on the CRF.

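### SAP deviation 5 applies one 3-month, 7-day look-back to every prohibited treatment, so boys barred by the protocol's longer windows stay in the per-protocol set

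*SAP*

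**What the plan says.** SAP Section 3 lists seven relevant protocol deviations. Number 5 opens "Treatment with prohibited medication (listed in Section 7.7.1 of Protocol", adds a minimum of 7 days of use, and sets the period as "at any time during the study or during the 3-month period prior to initiation of study treatment". The same section groups deviations 5, 6 and 7 as arising after treatment starts and lets those boys contribute until the deviation began. SAP 4.1.4 forms the per-protocol set from mITT boys with no relevant deviation. It adds one further exclusion, a baseline NSAA below 15.

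Protocol 7.7.1 sets windows item by item:

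- Anti-myostatin agents: "Prior exposure to RO7239361 or any other anti-myostatin agent", with no time limit.
- Gene therapy: "Concomitant or previous participation at any time in a gene therapy study".
- Exon skipping: "Treatment with exon skipping therapies within 6 months prior to the start of study drug administration".
- Ataluren, androgens and growth hormone: 12 weeks.
- Other investigational drugs: "currently or within 5 half-lives prior to the start of study drug administration".
- Any other drug not cleared by the medical monitor (item 7): 1 week before start, or during the study.

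No item carries a minimum duration. Protocol 6.2 excludes the same treatments apart from item 7. For other investigational drugs, however, 6.2 says "currently or within 12 weeks prior to the start of study drug administration". For growth hormone and androgens, the rationale in 3.1.2 says "currently or within 12 weeks or 5 half-lives (whichever is longer) prior to the start of study treatment", whereas 6.2 and 7.7.1 both say 12 weeks.

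**The concern.** Deviation 5 borrows the list in 7.7.1 but replaces its windows with a single shorter one and adds a duration threshold that the list does not have. The replacement is shortest relative to the protocol where the protocol looks back furthest. No other relevant deviation covers prior therapy, and the NSAA exclusion in SAP 4.1.4 does not touch it, so nothing else removes these boys.

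A per-protocol analysis is meant to show the result among boys who met the protocol's important conditions. Protocol 3.1.2 says that the effects of ataluren, exon skipping and investigational agents are poorly understood and could confuse interpretation, and Protocol 6.2 closes by insisting that every criterion be met. A set that retains boys with barred prior therapy answers that question less well. Leaving the rule loose also invites argument over membership after unblinding.

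**Working it through.** There is no stated figure to reproduce; the check compares two sets of rules.

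**Inputs.** Deviation 5: 3 months, at least 7 days (SAP Section 3). Item windows: Protocol 7.7.1. The SAP converts 6 months to 182 days in deviation 3, so 3 months is taken as 182 / 2 = 91 days (assumption). Twelve weeks is 12 × 7 = 84 days. Days of use are counted inside the window, because the SAP does not say how to count them (assumption).

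**Rule applied.** A boy whose continuous use ended on day −e is caught if 91 − e + 1 ≥ 7, that is, if e ≤ 85.

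| Prior history | Breaches 7.7.1? | Also in 6.2? | Caught by deviation 5? |
|---|---|---|---|
| Exon skipping stopped day −150 | Yes (182 days) | Yes | No |
| Anti-myostatin agent stopped day −365 | Yes (ever) | Yes | No |
| Gene-therapy participation ended day −365 | Yes (ever) | Yes | No |
| Androgen, 6 days, days −35 to −30 | Yes (84 days) | Yes | No |
| Uncleared other drug, days −5 to −1 | Yes (7 days) | No | No |
| Ataluren stopped day −84 | Yes | Yes | Yes |
| Ataluren stopped day −85 | No | No | Yes |
| Ataluren stopped day −86 | No | No | No |
| Uncleared other drug, days −23 to −14 | No | No | Yes, read literally |

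**Size of the exon-skipping gap.** Stop dates wholly outside the look-back run from day −92 to day −182: 182 − 91 = 91 days, or 91 / 182 = 50% of the window. If 3 months is meant as 12 weeks, the gap is 182 − 84 = 98 days, or 54%. The 7-day minimum adds stop dates −86 to −91 under the 91-day reading, giving 182 − 85 = 97 days, or 53%.

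**Wrongful removal.** Among ataluren stop dates, only day −85 meets the 84-day washout and still leaves 7 days inside 91. With 3 months as 90 days, the condition is 90 − e + 1 ≥ 7, so e ≤ 84, and no compliant ataluren user is caught. For item 7, Protocol 7.7.1 requires general medication on the CRF for only 4 weeks (28 days). The data needed for a literal removal therefore exist only for use ending about 8 to 28 days before start, and only for drugs that were not cleared.

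**Investigational-drug conflict.** The two washouts agree only where 5 × half-life = 84 days, a half-life of 84 / 5 = 16.8 days. At any other half-life, 6.2 and 7.7.1 give different answers.

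**The case against.** Protocol 10.2 leaves the SAP to describe major violations, and the SAP may legitimately choose a subset: the FVC, fracture and heart-failure exclusions are not relevant deviations either. Protocol Section 9 bars waivers and requires eligibility to be confirmed before randomization, so few such boys should enter. The SAP also uses 3 months loosely for 12 weeks elsewhere (4.7.1.3, on corticosteroid stability). All of this stands, and it limits the size of the point. It does not explain why a deviation that deliberately includes prior therapy should stop short of the three longest exclusions; the SAP gives no reason.

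A reader might infer that deviation 5 also removes compliant boys in any number. The documents do not support that. Section 3 classifies significant deviations already identified at sites, so a boy who met his washout may have nothing to classify. The reference to 7.7.1 can also be read as importing that section's own windows. What remains is the edge case shown above.

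A reader might also infer that every missed boy breaches 6.2, or that the rule retains those with the most persistent effects. Short use of an uncleared drug breaches only item 7 of 7.7.1. The documents say nothing about how long the effects of these therapies last; 3.1.2 calls the time course of the agents it names poorly understood.

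**Conclusion.** The point holds in one direction. Deviation 5 leaves in the per-protocol set boys whom Protocol 6.2 excludes for exon skipping that stopped about 3 to 6 months before Day 1, for anti-myostatin or gene-therapy exposure more than 3 months earlier, or for under 7 days of such use. The exon-skipping gap is 50% to 54% of the protocol window, depending on how 3 months is converted. The two any-time exclusions are missed for all exposure that ended before the look-back.

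The consequence is limited. The primary and secondary analyses use mITT (SAP 4.1.3, 4.4.1). The per-protocol MMRM is a sensitivity analysis, which Protocol 10.3.1 says will be done and SAP 4.4.4 makes optional. It would be wrong to infer that the primary NSAA result is at risk. The number of boys is not derivable. Purely as an assumption, 1 to 5 of the 159 planned would be 1 / 159 = 0.6% to 5 / 159 = 3.1%, and no effect on the estimate can be shown. The washout conflicts among 6.2, 7.7.1 and 3.1.2 are a separate inconsistency, relevant here because deviation 5 points to that list. The wording should be corrected before database lock.

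**What to change.** Split deviation 5 into two parts.

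1. Before treatment: any use of a treatment excluded in Protocol 6.2 within that treatment's own protocol window, with no minimum duration, leads to exclusion from the per-protocol set. State that participation in a gene-therapy study counts as such, not by days of use.
2. On treatment: use of a 7.7.1 prohibited treatment during the double-blind period, keeping the threshold of at least 7 days and the existing partial-inclusion rule.

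For item 7 (other uncleared drugs), keep a duration threshold and do not look back beyond its 1-week window. Otherwise a single over-the-counter dose would remove a boy.

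Separately, reconcile the windows for other investigational drugs (6.2 against 7.7.1) and for androgens and growth hormone (6.2 and 7.7.1 against 3.1.2), and refer deviation 5 to the reconciled list. This review does not say which window is right. At the same time, correct SAP 4.1.4, which cites Section 2.4 for a list that is in Section 3.

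The cost is SAP wording plus a protocol clarification. Prior DMD therapies are recorded on the CRF without a time limit. Other medication is required for only 4 weeks, so earlier androgen or growth-hormone use would have to come from eligibility records. The per-protocol set may change by a few boys.
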